7.1 Adverse events

An adverse event (AE) is any untoward medical occurrence (i.e., any unfavorable and unintended sign [including abnormal laboratory findings], symptom or disease) in a subject or clinical investigation subject after providing written informed consent for participation in the study. Therefore, an AE may or may not be temporally or causally associated with the use of a medicinal (investigational) product. Pre-existing medical conditions/diseases (i.e. Medical History(ies)) are considered AEs if they worsen after providing written informed consent. Abnormal laboratory values or test results constitute AEs only if they induce clinical signs or symptoms, or are considered clinically significant, or they require therapy.

The occurrence of adverse events should be sought by non-directive questioning of the subject at each visit during the study. Adverse events also may be detected when they are volunteered by the subject during or between visits or through physical examination, laboratory test, or other assessments.

All adverse events will be reported from the time the subject has provided informed consent to visit 14 (week 52). Starting from Week 76 (visit 15) until end of study, only AEs related to VAY736 and/or infection, potential malignant events and neutropenia will be recorded (only valid for AEs, not for SAEs).

Adverse events must be recorded on the Adverse Events CRF under the signs, symptoms or diagnosis associated with them, and accompanied by the following information:

1. the severity grade
 - mild: usually transient in nature and generally not interfering with normal activities
 - moderate: sufficiently discomforting to interfere with normal activities
 - severe: prevents normal activities
2. its relationship to study treatment
3. its duration (e.g. start and end date)
4. whether it constitutes a serious adverse event (SAE)
5. action taken regarding study treatment
6. whether other medication or therapies have been taken (concomitant medication/non-drug therapy)
7. its outcome

An SAE is defined as any AE which meets any one of the following criteria:

- is fatal or life-threatening
- results in persistent or significant disability/incapacity
- constitutes a congenital anomaly/birth defect

- requires inpatient hospitalization or prolongation of existing hospitalization, unless hospitalization is for:
 - routine treatment or monitoring of the studied indication, not associated with any deterioration in condition

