 - elective or pre-planned treatment for a pre-existing condition that is unrelated to the indication under study and has not worsened since signing the informed consent form
 - treatment on an emergency outpatient basis for an event not fulfilling any of the definitions of a SAE given above and not resulting in hospital admission
 - social reasons and respite care in the absence of any deterioration in the subject's general condition
- is medically significant, i.e. defined as an event that jeopardizes the patient or may require medical or surgical intervention to prevent one of the outcomes listed above.

All malignant neoplasms will be assessed as serious under “medically significant” if other seriousness criteria are not met.

Unlike routine safety assessments, SAEs are monitored continuously and have special reporting requirements; see [Section 7.2](#)

All adverse events should be treated appropriately. Treatment may include one or more of the following: no action taken (i.e. further observation only); study drug dosage adjusted/temporarily interrupted; study drug permanently discontinued due to this adverse event; concomitant medication given; non-drug therapy given. The action taken to treat the adverse event should be recorded on the Adverse Event CRF.

Once an adverse event is detected, it should be followed until its resolution or until it is judged to be permanent, and assessment should be made at each visit (or more frequently, if necessary) of any changes in severity, the suspected relationship to the study drug, the interventions required to treat it, and the outcome.

Information about common side effects already known about the investigational drug can be found in the Investigator Brochure (IB) or will be communicated between IB updates in the form of Investigator Notifications. This information will be included in the informed consent and should be discussed with the subject during the study as needed.

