9.5.2 Safety

Vital signs

All vital signs data will be listed by treatment, subject, and visit/time and if ranges are available abnormalities (and relevant orthostatic changes) will be flagged. Summary statistics will be provided by treatment and visit/time.

ECG evaluations

All ECG data will be listed by treatment, subject and visit/time, abnormalities will be flagged. Summary statistics will be provided by treatment and visit/time.

Clinical laboratory evaluations

All laboratory data will be listed by treatment, subject, and visit/time and if normal ranges are available abnormalities will be flagged. Summary statistics will be provided by treatment and visit/time.

Adverse events

All information obtained on adverse events will be displayed by treatment and subject.

The number and percentage of subjects with adverse events will be tabulated by body system and preferred term with a breakdown by treatment. A subject with multiple adverse events within a body system is only counted once towards the total of this body system.

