### Commercially Confidential Information

## 9 Statistical methods for safety and tolerability data

Open label VAY736 and the placebo data from before the patients were transferred to open label VAY736 will be presented as separate treatments in the outputs.

All data for background and demographic variables will be listed by treatment group and subject. Summary statistics will be provided by treatment group.

Subject disposition will be listed and summarized by treatment. In addition a figure displaying the subject disposition of all randomized subjects will be produced.

The number of subjects assessed by visit will be summarized in a frequency table and presented in a heatmap.

Relevant medical history, current medical conditions, results of laboratory screens, drug tests and any other relevant information will be listed by treatment group and subject. Data for study drug administration and concomitant therapies will be listed by treatment group and subject.

Boxplots to visualize trends in longitudinal safety data (vitals, ECG, lab parameter) will be created.

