### Adverse events

The number and percentage of subjects with adverse events will be tabulated by treatment, system organ class, and preferred term. Additionally the summary table with a breakdown by the severity of adverse events will also be provided. An adverse event starting at one time-point and continuing to another time-point will be counted only at the onset time-point. A

subject with multiple adverse events within a system organ class is only counted once towards the total of this system organ class.

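### SAP 9 counts a continuing adverse event only at onset, so a worsening after open-label VAY736 can be missing from the open-label column, and the tables are not limited to treatment-emergent events

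*SAP*

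**What the plan says.** SAP 9 sets the columns: "Open label VAY736 and the placebo data from before the patients were transferred to open label VAY736 will be presented as separate treatments". Under its Adverse events heading, the number and percentage of subjects with events "will be tabulated by treatment, system organ class, and preferred term". The SAP then adds: "Additionally the summary table with a breakdown by the severity of adverse events will also be provided". The counting rule for an event that spans time-points is: "An adverse event starting at one time-point and continuing to another time-point will be counted only at the onset time-point".

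Protocol 9.5.2 describes the same basic table ("The number and percentage of subjects with adverse events will be tabulated by body system and preferred term with a breakdown by treatment") and has no onset or worsening rule.

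On collection, Protocol 7.1 says: "All adverse events will be reported from the time the subject has provided informed consent". Once detected, an event is followed until it resolves or is judged permanent, and "assessment should be made at each visit (or more frequently, if necessary) of any changes in severity". Protocol 7.2 has progression of a known SAE sent in as follow-up to the original report, whenever it occurs.

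On the switch, Protocol 3.1 offers placebo patients open-label VAY736 from about one week after the Week 24 visit. Protocol 5.5.8 allows this earlier, after unblinding at Week 12 or later that follows a second increase in standard of care. These patients restart the visit schedule at Day 1 under a new patient number.

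**The concern.** A crossover patient contributes to two treatment columns, but an event that spans the switch is assigned by its start date alone. If it becomes worse after VAY736, that worsening is safety information about VAY736, and the stated rule gives it no place in the VAY736 column. An infection that is mild during the placebo period and severe after the infusion is the plain example.

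Safety and tolerability is a secondary objective, and Protocol 1.2 describes the trial as the first source of such information for VAY736 in this disease. The omission runs in one direction only: it can lower the open-label VAY736 counts and cannot raise them.

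A second, simpler gap is that nothing in the visible text keeps events that arise between consent and the first infusion out of the by-treatment tables.

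**Working it through.** The plan gives no figure on this point, so the check is textual, with one line of arithmetic for scale.

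**Step 1. Does the rule act across the switch?** It speaks of time-points, not treatment periods. The tables it governs are laid out by treatment, system organ class and preferred term, and no visit dimension is named. The change from placebo to open-label VAY736 is a change of column over time for the same person, so the rule reasonably applies there. This is an inference, but no other visible text governs the case.

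**Step 2. Would a worsening become a new event?** Protocol 7.1 has changes in severity assessed within an ongoing event, and Protocol 7.2 keeps SAE progression with the original report. The only statement in Protocol 7.1 that a worsening makes something an AE concerns pre-existing conditions, and its reference point is informed consent, not the open-label dose. The text leans towards one continuing event but does not settle the matter for non-serious events. It is also silent on how ongoing events carry over to the new patient number.

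**Step 3. Trace one illustrative event.** Suppose it is mild at onset on placebo, still mild at the open-label infusion, and severe afterwards.

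| Severity used in the table | Placebo column | Open-label column | Consequence |
|---|---|---|---|
| At onset | Mild | Not counted | Worsening in no summary table |
| Worst before transfer | Mild | Not counted | Worsening in no summary table |
| Worst over the whole event | Severe | Not counted | Worsening shown under placebo, against the pre-transfer limit |
| Worsening opens a new record | Mild | Severe | Correct, but no visible text requires it |

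In the first three rows the open-label column omits the worsening. In every row the patient counts once in placebo incidence, which is right because the event began there.

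**Step 4. Size.**
- Planned placebo patients: 6 (Protocol 3.1, SAP 2.2).
- If 32 are randomised at the overall 3:3:2 ratio (Protocol 5.2): 32 × 2/8 = 8.
- One omitted patient changes an open-label row by 1/6 = 16.7 percentage points if 6 cross over, or 1/8 = 12.5 if 8 do.
- Crossover is optional. If only 3 took it up (an assumption), the change would be 1/3 = 33.3 points.
- These figures assume that the patient has no other counted open-label event in the same row.

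**Step 5. Pre-dose events.** Screening runs from Day −28 to Day −1 in the assessment schedule, and AE collection starts at consent. Neither SAP 9 nor Protocol 9.5.2 sets a start date for tabulated events, so an event before any infusion can enter any treatment column. This step needs no assumption about the switch.

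**The case against.** The strongest reply is that this is a gap in wording and not a demonstrated misattribution. Several parts of it stand.

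- A reader might infer that the event is tabulated under placebo with the severity reached after VAY736. The documents do not support that as a statement of what the SAP does. It never says which severity is used, and it limits the placebo column to data from before transfer.
- A reader might also infer that placebo incidence is inflated by 17 points (12.5 with 8 patients). It is not. The event did start on placebo and is properly counted there. At most one patient changes row within the placebo severity table, and only if the worst severity over the whole event is used.
- The randomised 3 mg/kg and 10 mg/kg columns are untouched by the crossover issue, so a claim that VAY736 looks safer throughout would go too far.
- A cytopenia that worsens after the switch is a limited example. The open-label exclusions in Protocol 4.2 are blood-count limits, so only milder cases could cross over. The infection example is not limited in this way, because the listed open-label criteria contain no re-check for ongoing infection.
- Protocol 9.5.2 also displays all AE information by treatment and subject, so with so few patients an event that spans the switch could be traced by hand.
- Pre-dose events should not systematically favour an arm. They add noise.

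It can also be said that the table shells and derivations in RAP Modules 7 and 8, which are not available here, or redacted text may hold a rule. That is possible. But SAP 1.1 makes Module 3 the place for statistical methodology, and assigning events to treatments is methodology. The counting rule stands in Module 3 without a qualification.

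**Conclusion.** The point holds as a possible under-count in one column. Under the onset-only rule, an event that begins on placebo and worsens after open-label VAY736 is not counted under open-label VAY736. Depending on the unstated severity convention, the worsening is either absent from the summary tables or placed under placebo in conflict with the SAP's own column definition. One patient is worth 16.7 points in a 6-patient column or 12.5 in an 8-patient column, and more if fewer cross over.

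This rests on two assumptions: that the rule applies across the treatment switch, and that a worsening is kept within the original event record. If worsenings are in fact recorded as new events, the under-count disappears, but the SAP should say so. The absence of a treatment-emergent restriction depends on neither assumption. In a non-confirmatory trial with descriptive safety tables this is a moderate matter, worth correcting before database lock because a stated rule can lose drug-associated worsening.

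**What to change.** In SAP 9, Adverse events:

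1. Tabulate treatment-emergent events, defined as onset, or worsening in severity or seriousness, after the start of each infusion.
2. For crossover patients, use the worst severity up to the open-label infusion in the placebo column, and count any later worsening in the open-label VAY736 column. Limit the onset-only rule to continuation without worsening.
3. State which severity enters the severity table: the worst within the treatment period.
4. State how events ongoing at the switch are linked across the old and new patient numbers.
5. List events between consent and the first infusion separately, outside the treatment tables.

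The cost is SAP wording and derivation code. The eCRF must also hold the date of each severity change or open a new record on worsening. If it does neither at present, sites would have to supply those dates for the few crossover patients with events ongoing at the switch. Sample size and the efficacy analyses are unaffected.

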### **Vital signs**

All vital signs data will be listed by treatment, subject, and visit/time and if ranges are available abnormalities (and relevant orthostatic changes) will be flagged. Summary statistics will be provided by treatment and visit/time.

### **ECG evaluations**

All ECG data will be listed by treatment, subject and visit/time, abnormalities will be flagged. Summary statistics will be provided by treatment and visit/time.

### **Clinical laboratory evaluations**

All laboratory data will be listed by treatment, subject and visit/time. If normal ranges are available abnormalities will be flagged. Summary statistics will be provided by treatment and visit/time.

Commercially Confidential Information

### **Standard of care medication**

Data will be summarized together with changes from baseline and presented graphically in mean (SD) profile plots.
